10.3.3. Recording and Follow-Up of AE and/or SAE

AE and SAE Recording

- When an AE/SAE occurs, it is the responsibility of the Investigator to review all documentation (e.g., hospital progress notes, laboratory reports, and diagnostics reports) related to the event.
- The Investigator will then record all relevant AE/SAE information in the CRF.
- It is **not** acceptable for the Investigator to send photocopies of the subject's medical records to the Sponsor or designee in lieu of completion of the AE/SAE CRF page.
- There may be instances when copies of medical records for certain cases are requested by the Sponsor or designee. In this case, all subject identifiers, with the exception of the subject number, will be redacted on the copies of the medical records before submission to the Sponsor or designee.
- The Investigator will attempt to establish a diagnosis of the event based on signs, symptoms, and/or other clinical information. Whenever possible, the diagnosis (not the individual signs/symptoms) will be documented as the AE/SAE.

Assessment of Severity

AE severity will be evaluated by the Investigator in accordance with the NCI CTCAE v5. 0¹. For AEs that are not adequately addressed in the NCI CTCAE, the Investigator should classify the intensity of the AE using the following guidelines:

Grade 1: Mild: Aware of sign or symptom, but easily tolerated; no intervention needed

Grade 2: Moderate: Discomfort enough to cause interference with usual activity, minimal non-invasive intervention indicated (e.g., short course of antibiotics)

Grade 3: Severe: Medically significant but not immediately life-threatening; incapacitation with inability to work or do usual activity

Grade 4: Life-threatening: Refers to an event in which the subject was at risk of death at the time of the event, as judged by the Investigator; urgent/emergent drug indicated. This category should not be used for an event that hypothetically might have caused death if it were more severe.

Grade 5: Fatal outcome.

An event is defined as ‘serious’ when it meets at least 1 of the predefined outcomes as described in the definition of an SAE, NOT when it is rated as severe.

Assessment of Causality

- The investigator is obligated to assess the relationship between study intervention (investigational drug and/or study procedures) each occurrence of each AE/SAE according to the categories below.
- A “reasonable possibility” of a relationship conveys that there are facts, evidence, and/or arguments to suggest a causal relationship, rather than a relationship cannot be ruled out.
- The investigator will use clinical judgment to determine the relationship.
- Alternative causes, such as underlying disease(s), concomitant therapy, and other risk factors, as well as the temporal relationship of the event to study intervention administration will be considered and investigated.
- The investigator will also consult the Investigator’s Brochure (IB) and/or Product Information, for marketed products, in his/her assessment.

¹ Please refer to the CTCAE v5 at:

https://ctep.cancer.gov/protocolDevelopment/electronic_applications/docs/CTCAE_v5_Quick_Reference_5x7.pdf.

[Accessed April 19, 2019](#)

- For each AE/SAE, the investigator **must** document in the medical notes that he/she has reviewed the AE/SAE and has provided an assessment of causality in terms of whether the AE/SAE may be related to study intervention and/or study procedures.
- There may be situations in which an SAE has occurred, and the investigator has minimal information to include in the initial report to the Sponsor. However, **it is very important that the investigator always assess causality for every event before the initial transmission of the SAE data to the Sponsor**
- The investigator may change his/her opinion of causality in light of follow-up information and send a SAE follow-up report with the updated causality assessment.
- The causality assessment is one of the criteria used when determining regulatory reporting requirements.

Causality Categories:

Related: The AE follows a reasonable temporal sequence from the time of study drug administration and/or follows a known response to the study drug and cannot be reasonably explained by other factors such as the subject's clinical state or other therapeutic interventions, or concomitant drugs administered to the subject.

Not related: The AE is clearly related to other factors such as the subject's clinical state, therapeutic interventions or concomitant drugs administered to the subject. There is no temporal relationship between the study drug and event onset. This is especially so when an event occurs prior to the commencement of treatment with the study drug.

Follow-up of AEs and SAEs

- The Investigator is obligated to perform or arrange for the conduct of supplemental measurements and/or evaluations as medically indicated or as requested by the Sponsor or designee to elucidate the nature and/or causality of the AE or SAE as fully as possible. This may include additional laboratory tests or investigations, histopathological examinations, or consultation with other health care professionals.
- If a subject dies during participation in the study or during a recognized follow-up period, the Investigator will provide the Sponsor with a copy of any postmortem findings including histopathology, if available.
- New or updated information will be recorded in the originally completed CRF.
- The Investigator will submit any updated SAE data to the Sponsor or designee within 24 hours of receipt of the information.

10.3.4. Reporting of SAEs**SAE Reporting to Medical Monitor via an Electronic Data Collection Tool**

- The primary mechanism for initial reporting of an SAE to Sponsor or designee will be the electronic case report form (eCRF).
- If the eCRF is unavailable, then the site will use the paper SAE data collection tool (see next section) in order to report the event within 24 hours.
- The site will enter the SAE data into the eCRF as soon as it becomes available.
- After the study is completed at a given site, the eCRF will be taken off-line to prevent the entry of new data or changes to existing data.
- If a site receives a report of a new SAE from a study subject or receives updated data on a previously reported SAE after the electronic data collection tool has been taken off-line, then the site can report this information on a paper SAE form (see next section) or to the Medical Monitor by telephone.
- Contacts for SAE reporting can be found in the relevant site manual.

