8.3.1. Time Period and Frequency for Collecting AE and SAE Information

[Table 7](#) below summarizes the different reporting periods for AEs and SAEs.

Table 7: Adverse Event Reporting Periods

Type of Event	Adverse Event	Serious Adverse Event
Reporting period	From consent until Day 28 visit (at least 18 days after last dose of study drug).	From consent until Day 28 visit (at least 18 days after the last dose of study drug). SAEs will be recorded for study drug and for remdesivir.
Reporting Timelines to the Sponsor	Entered into the clinical database on an ongoing basis	Within 24 hours of site awareness

Medical occurrences that begin before the start of study drug but after obtaining informed consent will be recorded on the Adverse Events section of the case report form (CRF) and will be identified in the analysis as non-treatment-emergent adverse events (non-TEAEs).

All SAEs (for study drug and for remdesivir) will be recorded and reported to the Sponsor or designee immediately and under no circumstance should this exceed 24 hours from site awareness, as indicated in Appendix 3 ([Section 10.3](#)). The Investigator will submit any updated SAE data to the Sponsor or designee within 24 hours of it being available.

Investigators are not obligated to actively seek AEs or SAEs after conclusion of the study participation. However, if the Investigator learns of any SAE, including a death, at any time after a subject has been discharged from the study, and he/she considers the event to be related to the study drug or study participation, the Investigator must promptly notify the Sponsor or designee.

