5.8.2. Adverse Events

Adverse events will be coded using the Medical Dictionary for Regulatory Activities (MedDRA). All AEs that occur on or after the date of first dose of study intervention will be considered Treatment Emergent Adverse Events (TEAEs), and will be summarized using frequency counts and percentages, with the number of participants in the safety set used as the denominator.

Summaries of TEAEs will be presented by treatment group, and overall, using the MedDRA level hierarchy (system organ class and preferred term) as follows:

- Overall TEAEs (i.e., regardless of intensity or relationship to treatment)
- TEAEs by NCI CTCAE intensity grade (Grade 1, 2, 3, 4, 5)
- TEAEs by relationship to study medication (related, not related)
- TEAEs leading to permanent discontinuation of study medication (i.e., action taken is drug withdrawn)
- TEAEs leading to permanent discontinuation of study medication (i.e., action taken is drug withdrawn) by relationship to study medication
- Serious TEAEs (SAEs)
- SAEs by relationship to study medication (related, not related)

Unless otherwise specified, at each level of summarization a participant will be counted once if they reported one or more events at that level of summarization. If more than one occurrence of an event is reported, the event of the worst intensity or the worst-case relationship assessment will be summarized.

In the case of an incomplete AE start date, determining if an AE is treatment emergent will be based on the following rules. If the day is missing and the month and year of an onset date are provided and on or after the date of randomization, the following rules will be applied.

- If month/year of the onset date is on or after the month/year of randomization, the AE will be considered treatment emergent.
- If month/year of the onset date is equal to the month/year of randomization, and the end date is present, the end date will be used to determine when the AE started. If the end date is on or after randomization, the AE will be considered treatment emergent; otherwise, if the AE stopped before randomization, then it will not be considered treatment emergent.
- If month/year of the onset date is equal to the month/year of randomization, and the end date is a partial date, the AE will be considered treatment emergent.

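### The two causality categories in Protocol 10.3.3 leave a gap and set a stricter test than the section's own standard, so related-event tables and expedited-report screening may under-call drug-related events

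*Protocol*

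**What the plan says.** Under Assessment of Causality, Protocol 10.3.3 obliges the investigator to classify each AE and SAE using the categories that follow. There are two.

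- *Related*: "The AE follows a reasonable temporal sequence from the time of study drug administration and/or" it "follows a known response to the study drug and cannot be reasonably explained by other factors". The other factors named are the subject's clinical state, other treatment and concomitant drugs.
- *Not related*: "The AE is clearly related to other factors such as the" same three. A separate sentence follows, with no connecting word: "There is no temporal relationship between the study drug and event onset". A third sentence says this applies especially to events before the first dose.

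The same section gives a general standard. A reasonable possibility "conveys that there are facts, evidence, and/or arguments to suggest a causal relationship, rather than a relationship cannot be ruled out". Neither category uses that term. The section also asks for clinical judgement, for alternative causes to be considered, and for a note on whether the event may be related. It says causality is one of the inputs that decide what must be reported to regulators.

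SAP 5.8.2 carries the two levels into its tables: "TEAEs by relationship to study medication (related, not related", and the same split for SAEs. TEAEs leading to discontinuation are also tabulated by relationship. The SAP has no rule for a missing or unclassifiable relationship.

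**The concern.** A two-level classification needs each event to belong to exactly one level. Here one level asks that no other reasonable explanation exist and the other asks that another explanation be clear. Between them lies an event with a plausible but unproven alternative. In hospitalized COVID-19 patients on several drugs, that is a realistic case.

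Suppose a laboratory abnormality starts during dosing, is judged worse than expected for COVID-19, and could be due to a concomitant drug, though not clearly so. The alternative keeps it out of *Related*; the lack of clarity keeps it out of *Not related*. Section 10.3.1 also makes the consequences of a suspected drug-drug interaction an AE. Such an event involves a concomitant drug by definition, so an investigator could regard it as explained by that drug even where study drug contributed.

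Sites must still tick a box. If they take the *Related* wording at face value and default to *Not related*, events with real evidence of a drug effect leave the related-TEAE and related-SAE tables and weaken the causality input to expedited reporting. If sites resolve the ambiguity differently, the field does not mean the same thing across the trial.

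**Working it through.** The plan gives no figure to reproduce: neither document states an AE rate or a share of related events. The check is therefore to enumerate the definitions.

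**Event types.** Take events with onset during dosing, so that a temporal sequence is present. Cross known response to study drug (yes, no) with alternative explanation (none, reasonable but not clear, clear): 2 × 3 = 6 types.

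**Readings of *Related*.**
- R1, the natural one: (temporal sequence or known response) and no other reasonable explanation. The types with no alternative qualify: 2 of 6.
- R2: temporal sequence, or (known response and no other reasonable explanation). Timing alone suffices: 6 of 6.

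**Readings of *Not related*.**
- N1: both sentences required (clear other cause and no temporal relationship). No on-treatment type qualifies: 0 of 6.
- N2: either sentence suffices. The types with a clear other cause qualify: 2 of 6.

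| Reading | Related | Not related | Fits neither | Fits both |
|---|---|---|---|---|
| R1 + N1 | 2 | 0 | 4 | 0 |
| R1 + N2 | 2 | 2 | 2 | 0 |
| R2 + N1 | 6 | 0 | 0 | 0 |
| R2 + N2 | 6 | 2 | 0 | 2 |

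Under R1 a gap remains even on the lenient reading of *Not related*, and it is exactly the two types with a reasonable but not clear alternative (6 − 2 − 2 = 2). Under R2 the gap closes only because every on-treatment event becomes *Related*; with N2, two types then fit both categories. No combination separates the six types cleanly.

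**Against the section's own standard.** The reasonable-possibility text asks for positive support for a causal link. It rejects mere inability to exclude one, but does not require other explanations to be excluded. Under R1 the *Related* category does. An event with supporting evidence and also a reasonable alternative meets the standard and fails the category. An event with only timing and a competing cause may fail both.

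**The case against.** The strongest reply is that investigators apply clinical judgement, and that *Not related* is not meant as a two-part test. Its remark that the wording applies especially to pre-dose events implies that some on-treatment events can be *Not related*. That stands: it favours N2 and reduces the gap from 4 to 2 of the 6 types. It does not close it, because the judgement must still be expressed in one of the two categories.

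Three stronger readings are tempting and not supported.

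- A reader might infer that most on-treatment events fall in the gap. No document gives a share, and the six types carry no weights. Section 10.3.1 also keeps expected COVID-19 progression, and disease-associated laboratory findings no worse than expected, out of the AE definition, so these never reach the causality step.
- A reader might infer that drug-related events will certainly be under-called. No default is written for ambiguous events, the required note asks only whether the event may be related, and R2 would over-call.
- A reader might infer that the drug-related troponin outcome is compromised. It is adjudicated by the DMC (Protocol 3, SAP 5.8.3), and Protocol 10.5 sends all troponin elevations and cardiac events to the DMC whatever the site's category.

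It is also fair to say that the main safety conclusions do not use this field. SAP 5.8.2 summarises all TEAEs and all serious TEAEs by arm regardless of relationship in a blinded trial, Protocol 8.3.1 sends every SAE to the sponsor within 24 hours, and SUSAR handling follows local requirements and sponsor policy (8.3.4).

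Protocol Table 7 says "SAEs will be recorded for study drug and for remdesivir", while the categories name study drug only. That raises a separate question about attribution to remdesivir and is not needed for this point.

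**Conclusion.** The point holds in a limited form. On the natural reading the two categories are not exhaustive: an on-treatment event with a reasonable but not clear alternative cause has no place. *Related* is also stricter than the reasonable-possibility standard beside it. The gap is 4 or 2 of 6 logical types under the natural reading of *Related*, and 0 of 6 under the other, where timing alone makes an event *Related*.

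The effect is confined to the by-relationship tables in SAP 5.8.2, one input to expedited reporting, and consistency between sites. Under-calling is a risk, not a certainty. It assumes that sites use the natural reading and send unplaced events to *Not related*. How many events this would move cannot be derived from the documents.

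**What to change.** Define both categories by one question. *Related*: yes, there is a reasonable possibility that study drug caused the event, meaning that facts, evidence or arguments point to it as a cause. *Not related*: no, there is not. Delete the condition that other factors must not reasonably explain the event and the condition about absence of a temporal relationship. Timing and alternative causes stay as things to weigh, as the section already says.

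In SAP 5.8.2, add before database lock that a missing or unclassifiable relationship is counted as related. This would match the SAP's existing rule that an event whose onset cannot be placed counts as treatment-emergent.

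SAP 5.10 says enrollment had completed and that the protocol is to be amended for a Phase 3 part. The new wording therefore belongs in that amendment. Judgements already recorded in Phase 2 would change only if sites reassess them; the SAP rule alone affects only missing or unclassifiable entries.

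The cost is a short text change in the protocol, matching eCRF guidance and one sentence in the SAP. The downside is that somewhat more events will be called related and need review for expedited reporting.

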10.4. Appendix 4: Contraceptive Guidance and Collection of Pregnancy Information

10.4.1. Definitions

Woman of Childbearing Potential (WOCBP)

A woman is considered fertile following menarche and until becoming post-menopausal unless permanently sterile (see below).

If fertility is unclear (e.g., amenorrhea in adolescents or athletes) and a menstrual cycle cannot be confirmed before first dose of study drug, additional evaluation should be considered.

Women in the following categories are not considered WOCBP

1. Premenarchal
2. Premenopausal female with 1 of the following:
 - Documented hysterectomy
 - Documented bilateral salpingectomy
 - Documented bilateral oophorectomy

For individuals with permanent infertility due to a medical cause other than the above, (e.g., Mullerian agenesis, androgen insensitivity), Investigator discretion should be applied to determining study entry.

Note: Documentation can come from the site personnel's review of the subject's medical records, medical examination, or medical history interview.

Postmenopausal female

- A postmenopausal state is defined as having had no menses for 1 year without an alternative medical cause.
 - A high follicle stimulating hormone (FSH) level in the postmenopausal range may be used to confirm a postmenopausal state in women not using hormonal contraception or hormonal replacement therapy (HRT). However, in the absence of 1 year of amenorrhea, confirmation with more than one FSH measurement is required.
- Females on HRT and whose menopausal status is in doubt will be required to use one of the non-estrogen hormonal highly effective contraception methods if they wish to continue their HRT during the study. Otherwise, they must discontinue HRT to allow confirmation of postmenopausal status before study enrollment.

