5. STUDY POPULATION

5.1. Eligibility Criteria

5.1.1. Inclusion Criteria

To be eligible for participation in this study, subjects must meet all the following:

Age

1. At least 18 years of age at the time of signing the ICF.

Type of Subject and Disease Characteristics

2. Hospitalized for COVID-19.
3. Diagnosed with COVID-19 as defined by having at least 2 of the following signs or symptoms within the past 2 days:
 - a. Fever defined as a body temperature of ≥ 38.0 °C oral, or ≥ 38.3 °C rectal, ≥ 37.7 °C forehead or ≥ 38.7 °C aural (axillary temperatures are not allowable);
 - b. Cough;
 - c. Fatigue;
 - d. Shortness of breath.
4. Radiographic evidence (chest x-ray or CT scan) of one the following:
 - a. Ground-glass opacities, or
 - b. Local or bilateral patchy infiltrates, or
 - c. Interstitial pulmonary infiltrates.
5. Oxygen requirements:
 - a. $SpO_2 \leq 94\%$ on ambient airOR
 - b. Requires supplemental oxygen administration by nasal cannula, simple face mask, or other similar oxygen delivery device.

Sex

6. Male and/or female subjects.

Contraception use by men or women should be consistent with local regulations regarding the methods of contraception for those participating in clinical studies.

7. All subjects (male or female) who are of childbearing potential must agree to use highly effective contraception during the study. Female subjects and male partners of female subjects must continue to use highly effective contraception for 30 days after the last dose of study drug. Female subjects should not donate oocytes during this time. Male subjects and female partners of male subjects must continue to use highly effective contraception for 90 days. Male subjects must agree not to donate sperm during this time.

Note: Abstinence is acceptable if this is the usual lifestyle and preferred contraception for the subject.

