6.6.2. Restricted Medications

Restricted medications are defined as medications which should be avoided, if possible; however, **they are not necessarily prohibited during this study**. If such medications are required, consider switching to another medication in the class that is not restricted. If a restricted medication is required, seek approval of the Medical Monitor and use with caution per approved product label.

- FDA EUA or compassionate use agent(s) (to be discussed with Medical Monitor)
- Chloroquine, hydroxychloroquine, azithromycin (*Note: prior to prescribing these medications, must seek approval of the Sponsor's Medical Monitor*)
- HIV anti-viral drugs
- H2 blockers and antacids will be allowed as long as they are administered 2 hours before or after administration of study drug.

BLD-2660 as a Perpetrator

CYP3A4

The following are examples of some CYP3A4 substrates whose exposure could be reduced due to induction of that enzyme; however, it is not all inclusive and subjects should be monitored for adverse effects of these and CYP3A4 substrates in general.

- HMG CoA reductase inhibitors: atorvastatin, cervistatin, lovastatin, and simvastatin.
Note: Subjects taking the above statins can be switched to any of the following medications: pravastatin (Pravachol), rosuvastatin (Crestor), pitavastatin (Livalo), and fluvastatin (Lescol). If subject is unable to switch statin medications for any reason, the investigator to consult with Sponsor's Medical Monitor.
- Benzodiazepines
- Immune modulators
- Cyclosporine
- Tacrolimus
- Calcium channel blockers
- Hormonal contraceptives (refer to [Section 10.4.2](#))

CYP1A2

The following are examples of some CYP1A2 substrates whose exposure could be reduced due to induction of that enzyme; however, it is not all inclusive and subjects should be monitored for adverse effects of these and CYP1A2 substrates in general.

- Non-steroidal anti-inflammatory drugs (NSAIDs): Acetaminophen, phenacetin, naproxen
- Anticoagulants: Warfarin
- Antiemetics: Ondansetron
- Tricyclic antidepressants: Clomipramine, doxepin, imipramine
- Selective serotonin and norepinephrine reuptake inhibitors (SSNRIs): Duloxetine, fluvoxamine
- Antipsychotics: Olanzapine
- Bronchodilators: Theophylline
- Calcium channel blockers: Verapamil

CYP2B6

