10.4.2. Contraception Guidance

Male Subjects:

Male subjects are eligible to participate if they agree to the following from informed consent, during the treatment period and for 90 days after the last dose of study drug:

- Refrain from donating sperm

PLUS, either:

- Be abstinent from heterosexual intercourse as their preferred and usual lifestyle (abstinent on a long term and persistent basis) and agree to remain abstinent

OR

- Must agree to use contraception/barrier as detailed below
 - Agree to use a male condom

Female Subjects:

- A female subject is eligible to participate if she is not pregnant or breastfeeding, and at least one of the following conditions applies:
 - Is not a woman of childbearing potential (WOCBP)

OR

- Is a WOCBP and using a contraceptive method that is highly effective (with a failure rate of < 1% per year), preferably with low user dependency (see table below), at least 28 days prior to Screening, during the intervention period, and for 30 days after the last dose of study drug, and agrees not to donate eggs (ova, oocytes) for the purpose of reproduction during this period. The investigator should evaluate the effectiveness of the contraceptive method in relationship to the first dose of study drug.
- A WOCBP must have negative serum pregnancy test (minimum sensitivity 25 IU/L or equivalent units of human chorionic gonadotropin [HCG]) within 72 hours prior to receiving the first administration of study drug.
- If a urine test cannot be confirmed as negative (e.g., an ambiguous result), a serum pregnancy test is required, and results must be negative. In such cases, the subject must be excluded from participation if the serum pregnancy result is positive.

Contraceptive use by men or women should be consistent with local regulations regarding the use of contraceptive methods for those participating in clinical studies.

Note: Ethinyl estradiol is the primary estrogen used in hormonal contraceptives. The progestin component consists of norethindrone, levonorgestrel, norgestrel, norethindrone acetate, ethynodiol diacetate, norgestimate, desogestrel, and drospirenone. As BLD-2660 is a weak CYP3A4 inducer, exposure to both the estrogen and progestin components in hormonal contraceptives may be decreased, resulting in an increased risk of pregnancy. As such, it is recommended that subjects who are on hormonal contraceptives for birth control should use an

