alternate means of contraception (condoms, diaphragms, IUD, other barrier methods, sexual abstinence, etc.) during participation in the study.

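### The protocol's contraception rules conflict in two places: hormonal methods for women who stay on HRT, and the standard set for men

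*Protocol*

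**What the plan says.** **Women on HRT.** Protocol 10.4.1 (Postmenopausal female) covers women on HRT whose menopausal status is uncertain. They "will be required to use one of the non-estrogen hormonal highly effective contraception methods if they wish to continue their HRT during the study". The next sentence gives the other route: "Otherwise, they must discontinue HRT to allow confirmation of postmenopausal status before study enrollment".

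**The interaction.** A Note, given both in 5.1.1 and in 10.4.2, describes BLD-2660 as a weak CYP3A4 inducer and says that "exposure to both the estrogen and progestin components in hormonal contraceptives may be decreased, resulting in an increased risk of pregnancy". It then recommends, without requiring, that subjects who rely on hormonal birth control turn to "alternate means of contraception (condoms, diaphragms, IUD, other barrier methods, sexual abstinence, etc.) during participation in the study". Section 6.6.2 lists hormonal contraceptives among the CYP3A4 substrates whose exposure could fall, and cross-refers to 10.4.2. That list stands under a section whose opening definition reads "Restricted medications are defined as medications which should be avoided, if possible".

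**Effectiveness standard.** For women of childbearing potential, 10.4.2 asks for a highly effective method, defined by a failure rate below 1% per year, until 30 days after the last dose.

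**Men.** Inclusion criterion 7 in 5.1.1 states: "Male subjects and female partners of male subjects must continue to use highly effective contraception for 90 days". Section 10.4.2 requires a man to refrain from sperm donation for 90 days after the last dose and, in addition, either to be abstinent or to meet this condition: "Agree to use a male condom".

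**The concern.** These are eligibility and safety rules for an investigational drug, and pregnancy is a mandatory reason to stop study drug (Protocol 7.2). They need to give the same answer wherever a site looks.

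For women, choosing a method without estrogen does not avoid the interaction that the protocol describes, because the Note names the progestin component too. A woman could follow 10.4.1 to the letter and rely only on a hormonal method, since the Note recommends an alternative but does not require one.

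For men, the answer to whether a condom is enough, and whether the partner has any obligation, depends on whether the site reads 5.1.1 or 10.4.2.

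**Working it through.** No arithmetic applies. The check is to set the sections side by side.

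| Question | One place | Another place | Agree? |
|---|---|---|---|
| May a woman who stays on HRT rely on a progestin method? | 10.4.1: such methods are required or, on a looser reading, accepted; the interaction is not mentioned | 5.1.1 and 10.4.2 Note: progestin exposure may fall and pregnancy risk rise, alternative recommended; 6.6.2: restricted class | No |
| Must the alternative method be highly effective? | 10.4.2, female subjects: failure rate below 1% per year | Note: lists condoms, diaphragms, IUD, other barriers and abstinence with no reference to that rate | Not linked |
| What must a man use? | Criterion 7: highly effective contraception | 10.4.2: abstinence or a male condom, no effectiveness standard | No |
| What must his female partner use? | Criterion 7: highly effective contraception | 10.4.2: nothing stated | No |
| How long after the last dose? | Criterion 7: 30 days for women, 90 days for men | 10.4.2: the same | Yes |

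**Row 1.** The phrase *non-estrogen hormonal* has two readings. It can mean a hormonal method without estrogen, in which case 10.4.1 requires a progestin method of any woman who stays on HRT. It can also mean any highly effective method other than an estrogen-containing one, in which case a progestin method is only one permitted choice. On either reading 10.4.1 accepts a progestin method as highly effective and does not point to the Note or to 6.6.2. The conflict does not depend on which reading is meant.

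**Row 2.** The Note does not say whether its alternatives replace the hormonal method or are added to it, nor whether they must meet the stated failure rate. Section 10.4.2 mentions a table of methods that is not in the text available for this review and may have been lost in conversion. No conclusion is drawn here about which methods qualify.

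**Rows 3 and 4.** The documents give no failure rate for condoms, so whether a condom meets the definition cannot be settled from them. The mismatch does not need that figure, because the partner's obligation appears in criterion 7 and is absent from 10.4.2.

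**The case against.** The other side has several fair points.

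- **The HRT rule is conditional.** Stopping HRT is the other route, so no woman is forced onto a hormonal method. This stands, but a woman who stays on HRT still meets the conflict.
- **Restricted does not mean banned.** Section 6.6.2 says that restricted medications are not necessarily prohibited, and asks for Medical Monitor approval and caution where one is needed. So the protocol does not require something that it forbids. This stands. What remains is that 10.4.1 directs women toward a class that another section says to avoid where possible, and says nothing of the approval step.
- **Mitigation exists.** The Note covers every subject using hormonal contraception for birth control, and 10.4.2 tells the investigator to evaluate the method's effectiveness. This lowers the risk but does not reconcile the wording.
- **A man can satisfy both sections.** A condom plus a highly effective partner method could meet both. The gap is that a site reading only 10.4.2 would not know to ask about the partner.

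A reader might go further in three ways that the documents do not support.

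1. *The protocol regards hormonal contraception as unreliable.* It says only that exposure may fall, with more risk of pregnancy. For men this does not arise at all, since nothing says that the drug affects condoms.
2. *A man using condoms alone could be dropped from the per-protocol set.* SAP 5.4 does class inclusion violations as major, but SAP 4 excludes from that set only for major violations that would affect assessment of the primary efficacy endpoints. Contraceptive method has no evident bearing on recovery or SpO2/FiO2.
3. *The Note lapses before the 30-day duty ends.* A last dose on Day 10 puts the end of that duty at Day 40, 12 days after the Day 28 visit that completes the study under Protocol 4.5. But Protocol 1.1 and 4.4 also count a 60-day post-study period in how long the study lasts for each subject. Besides, 5.1.1 and 10.4.2 state the 30-day duty independently of the Note.

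**Conclusion.** Two inconsistencies hold on the text alone. First, 10.4.1 accepts, and can be read as requiring, a class of method that 5.1.1, 10.4.2 and 6.6.2 caution about with this drug, and the recommended alternatives carry no link to the protocol's own effectiveness standard. Second, men face one standard in criterion 7 and a looser one in 10.4.2.

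Severity is minor. The documents do not say how many women are on HRT with uncertain menopausal status; few are likely among the 120 planned subjects. The men's mismatch can touch any male subject with a partner of childbearing potential. There is no effect on endpoints, power or type I error.

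The conclusion assumes that the missing table of methods does not itself resolve the conflict. SAP 5.10 says that Phase 2 enrollment has completed and that the sponsor plans to amend this protocol for a Phase 3 part, so the main practical value of the correction lies in that amendment, if it goes ahead.

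**What to change.** Before the protocol is amended for the planned Phase 3 part:

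1. Reconcile 10.4.1 with the Note in 5.1.1 and 10.4.2 and with 6.6.2. Remove the double meaning of *non-estrogen hormonal*, and have each place refer to the others.
2. State how the Note's alternatives relate to the effectiveness standard in 10.4.2.
3. Reconcile criterion 7 with the male-subject text of 10.4.2, so that men and their partners have one standard, stated the same way in both places.

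Which methods are acceptable is for the sponsor's clinical team; this review proposes none. The cost is protocol wording in an amendment, with no added procedures, data collection or analysis.
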